7.3 Statistical Methods

7.3.1 Baseline Data

Baseline and demographic characteristics will be summarized by standard descriptive summaries (e.g. means and standard deviations for continuous variables such as age and percentages for categorical variables such as gender).

7.3.2 Efficacy Analysis

The primary purpose of this study is feasibility and acceptability. This will be assessed using the following data:

Qualitative data Analysis of audio recordings of end-of-treatment interviews will be completed by listening to files and taking detailed notes to highlight satisfaction, treatment experience, and suggested changes of intervention participants.

Survey data from the Client Satisfaction Questionnaire (CSQ-8) will be summarized using descriptive statistics. Exploratory analyses by race, gender, and housing circumstances will be done to look for any patterns.

Communication and treatment contact data will also be examined by creating summary counts of the number and types of communication (by modality and initiator), total minutes of completed treatment, and any notes from treatment sessions.

Clinical outcome analyses will focus on exploratory analyses to determine any evidence as to whether D-HOMES had clinically meaningful effects. We will assess planned future

primary behavioral and clinical outcomes of medication adherence (ASK-12) and point of care Hemoglobin A1c as detailed above. We will use t-tests to assess changes in these continuous variables in exploratory post-treatment analyses.

We will additionally use chi-squared tests (for categorical variables) and t-tests (for continuous variables) to examine within participant effect sizes and response rates (using standard cut offs) on the secondary end points listed above. We will analyze data in an intent-to-treat manner.

Exploratory analysis of electronic medical record and administrative claims data will examine the impact of various algorithms for constructing pharmacy-record adherence measures and health care use variables. We will use these analyses to define protocols for use in our Aim 3 randomized pilot.

7.3.3 Pharmacokinetic Analysis *Not applicable.*

7.3.4 Safety Analysis *Not applicable since there is no control group in this study.*

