Subject Population	We will enroll adults (age \geq 18 yrs.) with type 2 diabetes who are experiencing homelessness.
Key Criteria for Inclusion and Exclusion:	
Inclusion criteria:
 
 1. Age 18 yrs. or older 2. English-speaking 3. Homelessness by federal definition in the last 12 mo. 4. Self-reported diagnosis of type 2 diabetes, later verified in medical record 5. Plan to stay in local area or be reachable by phone for the next 16 weeks 6. Willingness to work on medication adherence and diabetes self-care 
Exclusion criteria:
 
 1. Inability to provide informed consent (e.g., presence of a legal guardian, prisoners) 2. Active psychosis or intoxication precluding ability to give informed consent 3. Pregnant or lactating females. 4. Patients who choose to opt out of research.
Number Of Subjects	
Total Number of Subjects: 15
 
Total Number at Hennepin Healthcare: Unknown
 
Total Number of Sites: 1 (Health Care for the Homeless)

Study Duration	
Each subject's participation will last 16 weeks.
 
The entire study is expected to last one year.

Study Phases	(1) Screening : screening for eligibility and obtaining consent, baseline assessment
Screening	
Intervention	(2) Intervention : study intervention with counselor support approximately weekly in-person and/or by phone x 12 weeks
Follow-Up	(3) Follow-up : final assessment
Efficacy Evaluations	
 • Self-reported medication adherence • Self-reported psychological wellness • Self-reported diabetes self-management, distress • Hemoglobin A1c measured by point-of-care fingerstick
Safety Evaluations	Not applicable in this single arm trial
Statistical And Analytic Plan	The primary endpoint of this study is the feasibility and acceptability of the program to participants in this treatment development phase. We will summarize themes in the end-of treatment interview, assess satisfaction via structured survey, and

assess treatment dose received via frequency, length, and type of communications with study staff.

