6.3 Pharmacokinetic Evaluation *Not applicable*

6.4 Safety Evaluation

Subject safety will be monitored by adverse events and rates of early termination of the study. We will also follow safety protocols in case we identify dangerous blood pressure, or heart rate values at baseline or final assessment visits. See Section 8 for details.

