7 STATISTICAL CONSIDERATIONS

7.1 Primary Endpoint

The primary endpoint of this study is the feasibility and acceptability of the program to participants in this treatment development phase. We will assess this by measuring our ability to recruit and retain participants, the dose of treatment we can deliver (i.e., participant's attendance and follow-up with scheduled sessions and treatment activities), and participants' report of their satisfaction and overall experience during participation in a structured survey (CSQ-8) and qualitative interview. In addition to above outcomes, we will

carefully track the number and types of between-treatment communications with participants (who initiated communication; form of communication: text, calls, e-mails, etc.).

We will conduct exploratory analyses to define our eventual primary behavioral endpoint of medication adherence e.g.) Change from baseline to 12-weeks in the ASK-12 questionnaire or Change from baseline to 12-weeks in ARMS-D questionnaire to help inform the next phase of the study. We will compare this with change in our eventual primary clinical endpoint of point-of-care Hemoglobin A1c during this same time frame.

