7.2 Secondary Endpoints

Secondary endpoints will include the following changes from baseline to 12-week visit: Overall change in patient-reported outcome measures: E.g.) Change in overall DSMQ score and changes in sub-scales E.g.) Change in Diabetes Distress score, E.g.) Change in health-related quality of life and psychological distress

Change in medication refill pattern from the electronic health record abstraction and insurance claims

Change in blood pressure, BMI

Safety and tolerability of the treatment based on Adverse Events and participant withdrawal

Exploratory analyses will examine the impact of different algorithms on claims data variable specification to define medication adherence, health care use (clinic, hospital, and emergency department), as well as to categorize when use related to diabetes overall and specifically to hypo- and hyperglycemic events necessitating hospitalization.

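### Adverse events are part of a secondary endpoint in 7.2, but 7.3.4 and the synopsis rule out a safety analysis for want of a control group, so they have no workable analysis

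*Combined protocol and SAP*

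**What the plan says.** Section 7.2 (Secondary Endpoints) includes the line "Safety and tolerability of the treatment based on Adverse Events and participant withdrawal". Section 6.4 (Safety Evaluation) agrees with it: "Subject safety will be monitored by adverse events and rates of early termination of the study". Section 8 (Safety Management) adds monitoring during the study, Adverse Events Forms and reporting to the IRB.

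Two entries point the other way. Section 7.3.4 (Safety Analysis) reads in full "Not applicable since there is no control group in this study", and the Safety Evaluations row of the synopsis reads "Not applicable in this single arm trial".

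Section 7.3.2 (Efficacy Analysis) has one general sentence on secondary endpoints. It uses chi-squared tests for categorical variables and t-tests for continuous ones "to examine within participant effect sizes and response rates (using standard cut offs) on the secondary end points listed above". The same section treats other uncontrolled data descriptively: "Client Satisfaction Questionnaire (CSQ-8) will be summarized using descriptive statistics", and communications are to be reported as counts by type and initiator.

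**The concern.** The plan declares an endpoint and then says, in the section where its analysis should be, that none applies. The reason given does not support that. Lack of a comparator limits what can be concluded about cause. It does not stop anyone reporting how many participants had an event, and the plan does not apply the same reasoning to its other single-arm data.

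At stake is a usable result for the randomised pilot that this study is meant to inform. Section 9.4.2 accepts that a minority of participants may have worsening mental illness, depression or suicidality during the study, while saying there is no evidence that taking part would cause this. A simple tally of events is the kind of information a pilot team would want to carry forward. Followed as written, the plan does not produce one as a study result.

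**Working it through.** The plan states no adverse-event rate and no statistical basis for its sample size, so there is no figure to reproduce. The check is mainly a comparison of the text.

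**Step 1: which entries conflict.**

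| Place | Position on safety |
|---|---|
| 7.2 | Secondary endpoint with two components: adverse events, withdrawal |
| 6.4 | Monitored through adverse events and early-termination rates |
| 8.1, 8.2 | Events monitored, recorded on forms, reported to the IRB |
| 7.3.4 | Analysis not applicable; reason: no control group |
| Synopsis | Evaluations not applicable; reason: single arm |

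The first three agree with one another. The last two conflict with them.

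**Step 2: does the general sentence in 7.3.2 fill the gap?** By its wording it reaches every endpoint in 7.2. To apply it, one needs either a baseline value for a within-participant change or a standard cut-off that defines a response. The documents give neither for adverse events arising on study. The section specific to safety also says that no analysis applies. The sentence is therefore nominally in scope but cannot be carried out for this component.

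**Step 3: does Section 8.2 fill the gap?** It sends serious events to the IRB within 24 hours, and a summary of notable non-serious events at continuing review. That is oversight reporting. It names no count or proportion of participants as an endpoint result.

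**Step 4: is the observation period settled?** No.
- The lead-in to 7.2 frames all listed items as changes between baseline and the 12-week visit, which does not fit events accruing over time.
- Section 8.1 monitors events for the whole study, and 5.7 also records serious, related events learned of after completion or withdrawal.
- Section 4.3.1 describes a 2-week run-in, 12 weeks of sessions and a 4-week completion window: 2 + 12 + 4 = 18 weeks, against a stated maximum of 16. Leaving out the run-in gives 12 + 4 = 16. Section 5.2 instead describes 2 weeks of assessment before and 2 after: 2 + 12 + 2 = 16.

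**Step 5: extent.** Section 7.2 has four endpoint lines: patient-reported outcomes, refill pattern, blood pressure and BMI, and safety. One of the four is affected and, within it, one of two components.

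**Step 6: what a single-arm summary could show.** These figures describe precision after the fix, not the size of the defect. Input: N = 15 (synopsis). Event counts, true rates and smaller sample sizes are assumptions.
- One affected participant: 1/15 = 6.7%, exact (Clopper-Pearson) 95% interval 0.2% to 31.9%.
- None affected: two-sided 95% upper limit = 1 − 0.025^(1/N). For N = 15 this is 21.8%. Section 4.3.2 allows enrolment to stop before 15: N = 12 would give 26.5% and N = 10 would give 30.8%.
- Chance that no participant of 15 has an event, (1 − p)^15: 46.3% for p = 5%, 20.6% for p = 10%, 3.5% for p = 20%.

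All of this can be computed without a control group.

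**The case against.** The strongest reply is that the plan does state a method. The chi-squared and t-test sentence refers to the secondary endpoints as listed, and safety is on the list. This stands as a limit on the claim. A reader might infer that no analysis of any kind is stated for this endpoint, and the documents do not support that. What they support is that the stated method cannot be applied to adverse events.

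A second reply is that the data will exist. Events are monitored and put on forms, and about 15 people could be tabulated at any time. This also stands. A reader might infer from the two not-applicable entries that safety is unmonitored, but 6.4, Section 8 and the monitoring plan in 9.4.1 show otherwise. It keeps the point minor but does not remove the contradiction.

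A third reply is that withdrawal, the other half of the endpoint, is covered. It largely is. Section 7.1 says of the primary endpoint "We will assess this by measuring our ability to recruit and retain participants", and 6.4 names early-termination rates. A reader might take the whole safety line to be unanalysed; the gap is in the adverse-event component.

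Finally, the contradiction could be closed by deleting adverse events from 7.2 and leaving them to Section 8. That would be consistent, but it would give up a result the authors chose to declare, to save one small table.

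**Conclusion.** The point holds as a minor defect of consistency and reporting. One component of one of four secondary endpoint lines has no workable analysis, because two entries dismiss safety analysis for a reason that excludes only a between-group comparison. The feasibility and acceptability conclusions do not depend on it, and the study is expected to be classed as minimal risk (9.4.1).

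The conclusion rests on reading 7.2 as a genuine list of endpoints and 7.3.4 as the governing statement on their safety analysis. It assumes nothing about how many events will occur. It does not imply unsafe conduct or a missing oversight system.

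**What to change.** Reconcile the two not-applicable entries (synopsis and 7.3.4) with 6.4, 7.2 and Section 8. Replace them with a single-arm descriptive summary giving the number and proportion of enrolled participants with any adverse event, the number and proportion with any serious adverse event, and the number of early terminations.

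State the observation period for these counts explicitly. The baseline-to-12-week framing in 7.2 should be lifted from the safety line, and the durations in 4.3.1 and 5.2 must be reconciled so that the start and end of the period are unambiguous.

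The cost is a few sentences in 7.3.4 and the synopsis, a small edit to 7.2, and one table built from the Adverse Events Forms that 8.2 already provides for. No new data collection is needed for these counts. The downside is imprecision: with 15 participants the proportions will have wide intervals, and the text should say in advance that zero events will not be presented as evidence of safety.

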7.4 Sample Size and Power

This sample size is appropriate for the goal of treatment development and protocol refinement. This is in line with ongoing studies by [name] (HSR#17-4351) as well as the current literature.¹¹⁰

8 STUDY MEDICATION (*Not applicable*)

8 SAFETY MANAGEMENT

8.1 Clinical Adverse Events

Clinical adverse events (AEs) and serious adverse events (SAEs) will be closely monitored throughout the study in accordance with HHRI IRB definitions and policies.

8.2 Adverse Event Reporting

Unanticipated problems related to the research involving risks to subjects or others that occur during the course of this study and SAEs will be reported to the IRB in accordance with IRB Attachment EEE: Prompt Reporting Guidelines. AEs that are not serious but that are notable and could involve risks to subjects will be summarized and submitted to the IRB at the time of continuing review.

[name] will be responsible for completing Adverse Events Forms should an event occur. She will report Serious Adverse Events to the HHRI IRB within 24 hours of having received notice of the event.

Drs. [name], [name], and [name] will collaboratively gather any information needed to investigate the event and determine subsequent action. Any subsequent action will be documented and reported to the HHRI IRB and the Program Officer at NIH.

Adverse event reports will be reviewed annually with the HHRI IRB to ensure participant safety.

8.3 Investigator Reporting of a Serious Adverse Event to Sponsor

Reporting to the National Institutes of Health will be completed as required by their policies or advised by HHRI IRB staff.

8.4 Medical Emergencies

If non-urgent psychological distress arises in participants during study related activities, study staff will provide a handout about local mental health resources, including a 24-hour support line and psychiatric emergency room (Appendix P). If non-urgent physical health needs arise in participants, study staff will provide written resources about health care available through Health Care for the Homeless and Hennepin Healthcare (Appendix P). If an emergency physical or behavioral health situation arises, study staff will arrange for immediate clinical support from PI ([name]), Health Care for the Homeless clinical staff (who have a walk-in treatment model), the Hennepin County mental health crisis team (COPE Line, available by phone or in-person 24hrs./day, 7 days/week), or emergency medical services as appropriate. This event will be written up and reviewed by the PI ([name]) and primary mentor ([name]) within 48 hours of the event and reported to the IRB if needed.

If measured blood pressure surpasses SBP>180 or DBP>100 or pulse>150 or if blood sugar measurement takes place within a study visit and falls <60 or >400/error, study staff will page [name] who will provide clinical assessment of symptoms and make referral or arrangement for immediate transfer to appropriate treatment as needed.

As deemed necessary by the primary mentor and/or HHRI IRB, issues related to patient safety will be reviewed with mental health or medical professionals at HCMC not affiliated with the study who will provide recommendations for withdrawal from the study, referrals for additional care, or other necessary action.

9 STUDY ADMINISTRATION

9.1 TREATMENT ASSIGNMENT METHODS

9.1.1 Randomization or Other Assignment *No randomization will occur in this single arm trial.*

9.1.2 Blinding *There will be no blinding.*

9.1.3 Unblinding *Not applicable*

9.2 Data Collection and Management

We will assign study ID numbers to all participants. Study IDs will be used on all study documents. Consent forms will be stored separately and will not be associated with study IDs when stored. Tracking forms will ensure each enrolled participant has a completed consent form.

Data from paper surveys administered during screening interviews and assessment visits will be entered and stored in REDCap. Physical copies of the surveys will be stored in a locked file drawer separate from consent documents. Electronic health record access will take place in Hennepin Healthcare EPIC or via faxed paper copies of medical records from other health systems. Data from electronic health records will be extracted by a trained research staff member and entered into standard forms using REDCap.

All treatment sessions and final close-out interviews will be audio recorded. Notes about treatment plans and notes summarizing main themes about satisfaction, treatment experience, and suggested changes will be created. Notes will remove all 18 HIPPA personal identifiers if mentioned. Notes will use only subject ID numbers and will contain no personal identifiers. Once audio recordings are uploaded to the HHRI-maintained

computer network, they will be deleted from the audio recording equipment. Audio recordings will be destroyed on or before the end of the grant period, 12/31/2023. Since assessment visits will be conducted at locations away from the research offices of the PI, extreme care will be taken to keep study materials in the possession of research staff at all times. Immediately after visits, consent forms, hemoglobin A1c results, audio equipment, and other study materials will be returned to the secure research offices of Hennepin Healthcare Research Institute. Each office has a locked door in a badge-access-only wing of the Institute. Signed consent documents will further be stored in a locked file drawer whose key will be stored in a separate locked key box.

Study data, including all audio recordings will be stored and analyzed on [name] and her staff's HHRI-maintained computer network. This network is robust, secure, and has state-of-the-art back-up and password protections. [name] and staff will comply with any necessary software, hardware, and data storage updates to maintain the security of this system under the direction of the HHRI IT Department.

The identifiers will be destroyed on or before the completion date of the grant, 12/31/2023. The other data will be retained for three years.

9.3 Confidentiality

All data and records generated during this study will be kept confidential in accordance with HHRI Institutional policies and HIPAA on subject privacy. The PI and other site personnel will not use such data and records for any purpose other than conducting the study.

Confidentiality will be maintained by numerically coding all data, disguising identifying information, and keeping data in secure electronic locations or locked in file drawers. All electronic data will be numerically coded and stored on a password protected computer in a secure research space. All paper forms will be stored in locked file cabinets in a locked room. Names of participants will be stored separately. Participant information will be accessible only to HHRI-trained research staff, who are pledged to confidentiality and complete training in the ethical conduct of research (i.e., both HIPAA and CITI trainings). Identifying information will not be reported in any publication.

No identifiable data will be used for future study without first obtaining IRB approval. The investigator will obtain a data use agreement between the provider (the PI) of the data and any recipient researchers (including others at Hennepin Healthcare) before sharing a limited dataset (PHI limited to dates and zip codes).

9.4 Regulatory and Ethical Considerations

9.4.1 Data and Safety Monitoring Plan

This treatment development study (N=15), does not meet NIH criteria requiring a Data Safety Monitoring Board (DSMB) as we expect it to be considered minimal risk by the HHRI IRB.

However, we have a detailed data safety and monitoring plan. [name] will have primary responsibility for monitoring all procedures for data collection, analysis, and storage. Any adverse events, breaches of confidentiality, or other data or safety issues that arise will be discussed during weekly visits with [name] (primary mentor) or sooner if required and immediately brought to the attention of [name] (biostats. co-mentor). [name] has served on numerous DSMBs for large NIH trials. If needed, Drs. [name] and [name] will locate representatives independent of the study team for input.

All issues related to patient safety (e.g., psychiatric distress) will be reviewed with medical and mental health professionals at Hennepin Healthcare not affiliated with the study who will provide recommendations for withdrawal from the study, referrals for additional care, or other necessary action.

If requested by NIH or our local IRB, a DSMB will be convened.

9.4.2 Risk Assessment

Discomfort or distress when completing assessment and treatment procedures. Some participants may feel uncomfortable or distressed answering personal or private questions during assessment or treatment. Some participants may also feel uncomfortable or distressed due to the collection of physical measures (e.g., weight). In previous studies by [name], when individuals did report discomfort in these situations, it was mild.

We minimize discomfort or distress with three key approaches: (1) clearly explaining the study and emphasizing the optional nature of participation, (2) conducting all treatment sessions and assessment visits in private settings, (3) staff training about the sensitivity of chronic health conditions and the specific circumstances of homelessness including how to offer appropriate support.

Confidentiality or loss of privacy. We will collect potentially sensitive information about participants; if released inappropriately, participants may experience embarrassment or distress. The seriousness of the consequences would depend on the nature of the information revealed and to whom the information was revealed. See Section 9.2 detailing the numerous steps we take to protect participant confidentiality. We therefore think the risk of a breach of confidentiality is low.

Worsening of mental illness, depression, and emergent suicidality. Circumstances of homelessness can be high stress. Although there is no evidence to suggest this would be exacerbated from trial participation, it is possible that a minority of participants will experience worsening of mental illness, depression, or episodes of suicidality during this study. See Section 8.4 above for our detailed safety plan to address this risk.

